### Introduction

Important cellular processes depend on iron and homeostasis of iron is well regulated. Furthermore, iron is essential for oxygen transport and storage, cardiac and skeletal muscle metabolism, energy production in the mitochondria, synthesis and degradation of proteins, lipids and ribonucleic acid, the correct functioning of immune and nervous systems [1]. Iron causes a protective effect in myocytes during hypoxia. Iron deficiency (ID) is more detrimental for the vitality of cardiomyocytes and skeletal myocytes during hypoxia, compared to iron excess [2]. ID directly affects function of the heart and leads to mitochondrial dysfunction and adversely affects cardiomyocyte contractility and relaxation [3]. ID has been shown to be an independent predictor of poor outcomes, irrespective of the presence of anaemia, in patients with heart failure (HF) [4-9].

Negative impact of ID on the left ventricular (LV) function, quality of life and outcomes in patient with acute coronary syndrome (ACS) has been shown [10-14]. However, the effects of ID treatment in patient with myocardial infarction (MI) has not been well studied.

### Methods

Proposed study uses an open-label prospective randomized single-center study approach. 360 patients, with or without ID, hospitalized with MI are recruited at the Kazan city clinical hospital №7, which is the clinical base of Kazan State medical university. Patients with ID (n=240) are randomised (1:1) to either intravenous (i.v.) FCM or oral ferrous sulphate. Patients with normal iron status (n=120) are in the control group.

The trial, which is conducted in strict compliance with Good Clinical Practice (GCP) and with the Declaration of Helsinki, was approved by the Local Ethics Committee.

**Study population.** Male and female patients aged  $\geq 18$  years, hospitalised with MI and diagnosed according to **Fourth Universal Definition of MI and Myocardial Injury (ESC 2018)**, with hypokinesia or akinesia in at least two connected LV segments according to echocardiography results obtained within the first 24 hours after myocardial infarction occurs, will be considered for participation. All patients who agreed to participate will be asked to provide written informed consent before any trial-related procedure is performed.

**Inclusion and exclusion criteria.** Inclusion/exclusion criteria are shown in Table 1

**Definition of MI.** MI is diagnosed according to **Fourth Universal Definition of MI and Myocardial Injury (ESC 2018)** when there is a rise and/or fall of cardiac troponin values (cTn) values with at least one value above the 99th percentile upper reference limit (URL) and at least one of the following signs: symptoms of myocardial ischaemia, new ischaemic ECG changes, development of pathological Q waves, imaging evidence of new loss of viable myocardium or new regional wall motion abnormality in a pattern consistent with an ischaemic aetiology [15].

**Definition of ID.** ID is defined as serum ferritin  $<100$  ng/mL (absolute ID) or  $100$  ng/mL  $\leq$  serum ferritin  $\leq 299$  ng/mL if transferrin saturation (TSAT)  $<20\%$  (functional ID) [9].

**Assessment of LV systolic function.** LV systolic function is assessed by transthoracic echocardiography with evaluation of Wall motion score index (WMSI) using 16-segment model [16].

**Assessment of quality of life.** Quality of life is assessed using the Kansas City Cardiomyopathy Questionnaire (KCCQ) [17]

**Screening.** During screening all risks and benefits of participation are described to each patient who fit the chosen inclusion criteria. Each patient considered in the study will be provided 2 copies of written consent and will receive one copy of the consent, in addition each patient will receive a form containing information about study participation. Anamnesis, physical examination, echocardiography, KCCQ, complete blood count (CBC), serum iron level, total iron binding capacity (TIBC), serum ferritin level, TSAT, alanine transaminase, aspartate transaminase, creatinine are performed at the screening visit within 24 hours after MI. The data of each study participant will be entered into individual patient registration cards specially designed for each visit.

**Randomisation and study treatment dosing regimen.** Patients with ID are randomised to either i.v. FCM or oral ferrous sulphate randomly with block randomizations. The FCM doses were determined using the patient's screening visit body weight measurement and haemoglobin value (table 2). Patients receives all doses during hospitalization accordance with the drug local

labels. 100 mg of ferrous sulphate is administrated 2 times per day during hospitalization and continue within next 2 month.

**Study outcomes.** The primary significant outcome is the decrease in WMSI value. The secondary outcome the composite of cardio-vascular (CV) mortality, non-fatal stroke, non-fatal MI, recurrent HF hospitalizations.

**Patient Assessments.** All participants are observed for 12 months from the first visit after the admission to the study. Participants are evaluated in-person at 3-, 6-, and 12-month intervals with correction of treatment if necessary. Participants are also evaluated monthly through telephone consultation. Echocardiography with WMSI evaluation, KCCQ, CBC, serum iron level, TIBC, serum ferritin level, TSAT is performed during every physical evaluation visit. Primary and secondary outcomes are established during follow up period.

**Statistical analysis.** Statistical data is analysed using standard methods of descriptive statistics. For categorical variables, summary tabulations of the number and percentage of subjects within each category of the corresponding parameter will be presented. For continuous variables, the mean, median, standard deviation, first and third quartiles, and minimum and maximum values will be presented. Clinical-laboratory associations will be assessed as well as associations with outcomes (Kaplan-Meier subgroup survival curves). The level of significance to be used for tests will be 0.05.

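### The plan names no groups, visit or between-arm analysis for WMSI, and its only named control group is the 120 non-randomised iron-replete patients

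*Combined protocol and SAP*

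**What the plan says.** Methods describes the design as follows: "Proposed study uses an open-label prospective randomized single-center study approach". Allocation applies to the iron-deficient patients only: "Patients with ID (n=240) are randomised (1:1) to either intravenous (i.v.) FCM or oral ferrous sulphate". The Randomisation paragraph confirms this, and both arms receive iron. The remaining patients are described in one sentence: "Patients with normal iron status (n=120) are in the control group".

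Under Study outcomes, "The primary significant outcome is the decrease in WMSI value". The secondary outcome is a clinical composite. Neither outcome is tied to a pair of groups. Under Patient Assessments, "Participants are evaluated in-person at 3-, 6-, and 12-month intervals", with WMSI obtained each time. On timing there is only this: "Primary and secondary outcomes are established during follow up period".

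The Statistical analysis paragraph begins "Statistical data is analysed using standard methods of descriptive statistics". It then lists summary statistics, unspecified associations, Kaplan-Meier curves by unnamed subgroups, and 0.05 as the level for tests it does not name.

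**The concern.** A reader who follows the plan as written cannot say which two groups the primary result compares, at which visit, or with what estimate. The one group given a comparator's name was formed by iron status, not by allocation.

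The Introduction gives the reason this matters: "Negative impact of ID on the left ventricular (LV) function, quality of life and outcomes in patient with acute coronary syndrome (ACS) has been shown". On the plan's own rationale, the iron-replete patients are expected to differ in prognosis from both treated arms. If an iron-treated arm were set against them and the difference read as an effect of iron, treatment and iron status would be mixed, and randomisation would give no protection. The direction is open. Worse prognosis in ID could hide a benefit; a worse starting WMSI with more room to fall could mimic one.

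Separately, three visits and an unstated contrast leave room to choose both after results by group are known. The open-label design makes early sight of such results easier, though it is not the source of the problem.

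**Working it through.** **Group sizes.** 240 + 120 = 360, the stated total; 240/2 = 120 per randomised arm. The figures agree. The plan gives no effect size, standard deviation or power, so there is no sample-size calculation to reproduce.

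**Comparisons that fit the text.** Three groups give 3 pairwise contrasts. With 3 follow-up visits that is 3 × 3 = 9 possible WMSI comparisons. Three are randomised (FCM versus oral iron at each visit); the other six involve the iron-replete group.

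**False-positive risk for the randomised contrast alone.** Inputs from the plan: three visits and a 0.05 level. Assumptions: two-sided tests (sidedness is not stated), normal test statistics, the same correlation ρ between any two visits, no true difference, and success declared if any visit is significant. The quantity is

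P(max |Z_j| > 1.96, j = 1, 2, 3), where each Z_j is standard normal and any two have correlation ρ.

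Simulation with 2,000,000 draws gives:

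| ρ | P(at least one visit significant) |
|---|---|
| 1 | 0.050 |
| 0.9 | 0.084 |
| 0.7 | 0.109 |
| 0.5 | 0.125 |
| 0 | 0.143 (= 1 − 0.95³) |

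**Which ρ is reasonable.** The outcome is a decrease, so all three values subtract from the same screening measurement. Let WMSI have variance s² at each time and correlation r between any two times. Each decrease then has variance 2s²(1 − r), and two decreases have covariance s² − s²r − s²r + s²r = s²(1 − r). Their correlation is s²(1 − r) / 2s²(1 − r) = 0.5. If follow-up scans correlate more with each other (q) than with the acute scan (r), it is (1 − 2r + q) / [2(1 − r)], which exceeds 0.5 when q > r. A range of 0.5 to 0.9 is therefore used, giving about 12.5% down to about 8%. The documents supply no correlation.

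**Contrasts with the iron-replete group.** No figure is given. A joint error rate over all nine comparisons would assume that the iron-replete and ID patients have equal prognosis, which the Introduction contradicts. A bias would need the prognostic difference in WMSI units and its standard deviation, and the documents give neither.

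**The case against.** The strongest reply is that the comparison is obvious. The study is called randomised, only FCM and oral iron are randomised, and no section proposes testing an iron arm against the iron-replete patients as a treatment effect. The talk of associations also fits an observational role for the 120. On this reading, *control* simply means a reference group, and the sentence that uses the word also defines it.

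Much of that stands. A reader might infer that the trial intends to estimate the effect of iron against the iron-replete group, or that the label is itself an error. The text supports neither: the label is not wrong in itself, and the confounded comparison is left open, not planned. A reader might also infer a false-positive risk of 14% or more. For the randomised contrast, 14% needs zero correlation between decreases that share one screening value, which is implausible.

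What does not stand is that implication is enough. An implied contrast is not a prespecified one, and it still leaves the visit and the estimate unstated. The text available here lacks the opening page, which might carry an objective naming the groups. That limits certainty about the contrast more than about the visit, since the paragraphs that define the outcome and its timing are present and silent.

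**Conclusion.** The point holds as a gap in specification with real consequences. The plan commits to no randomised effect estimate for WMSI or for the composite, and it fixes no primary visit. If FCM versus oral iron is taken as intended, the open visit alone raises the false-positive risk from 5% to about 8% to 12.5%, under the assumptions of two-sided tests, equal between-visit correlation of 0.9 to 0.5, and success claimed on any visit. This measures the latitude left open; it is not an error rate the plan states.

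Using the iron-replete group to estimate a treatment effect would add confounding by iron status, of unknown sign and size. The randomised comparison itself is sound and available; the plan needs to commit to it.

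**What to change.** In the Study outcomes and Statistical analysis paragraphs, state that:

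- The primary analysis is i.v. FCM versus oral ferrous sulphate in the 240 randomised ID patients, reported as a between-arm difference in WMSI with 95% CI at one visit.
- That visit is fixed before any comparison by group, for example 12 months, where the stated follow-up ends. The other two visits are supportive.
- The analysis is adjusted for WMSI from the screening echocardiogram. The Screening paragraph lists the echocardiogram without naming WMSI, so say that baseline WMSI is read from it. A prespecified repeated-measures model that gives the estimate at the chosen visit is equally acceptable.
- The composite uses the same contrast.
- The 120 are a non-randomised iron-replete reference cohort, compared descriptively or in explicitly observational analyses, and never as a treatment effect.
- The trial estimates FCM relative to oral iron, not iron versus no iron.

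The cost is wording only; recruitment, visits and data collection are unchanged. The downside is that WMSI at the two other visits becomes supportive, and contrasts with the iron-replete group can no longer be presented as treatment effects.

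### The primary outcome is a decrease in WMSI with no baseline-adjusted comparison stated; adjusting for screening WMSI would gain precision at no extra data collection

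*Combined protocol and SAP*

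**What the plan says.** All references are to the combined protocol and SAP, Methods.

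- **Study outcomes:** "The primary significant outcome is the decrease in WMSI value". No visit, arm contrast or summary measure is attached to it.
- **Assessment of LV systolic function:** "Wall motion score index (WMSI) using 16-segment model". The per-segment scores are not given.
- **Study population:** patients qualify "with hypokinesia or akinesia in at least two connected LV segments", on an echo "obtained within the first 24 hours after myocardial infarction occurs".
- **Screening:** the screening assessments, echocardiography among them, "are performed at the screening visit within 24 hours after MI". This is the only WMSI before treatment, so it is the implied baseline.
- **Methods, opening paragraph:** "Patients with ID (n=240) are randomised (1:1) to either intravenous (i.v.) FCM or oral ferrous sulphate", which is 120 per arm.
- **Randomisation:** "Patients with ID are randomised to either i.v. FCM or oral ferrous sulphate randomly with block randomizations". No stratification factor is mentioned.
- **Patient Assessments:** WMSI is repeated at 3, 6 and 12 months, and none of these is named as primary.
- **Statistical analysis:** descriptive statistics, Kaplan-Meier curves and a 0.05 level. No test, model or covariate is given for WMSI.

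**The concern.** WMSI has a floor at its normal value, so a patient's decrease cannot exceed the baseline excess over normal. The entry rule admits a wide range of baseline extent, from two hypokinetic segments upward. Patients with more abnormal segments on day 1 have more room to improve, and some of that improvement may occur whichever iron preparation is given. If the arms are compared on the decrease alone, the part of its spread that baseline extent predicts stays in the error term, although screening WMSI is known for every patient before randomisation.

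What is at stake is the power of the trial's main comparison and its sensitivity to a chance difference in baseline WMSI between arms. Unstratified blocks balance baseline WMSI only on average.

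**Working it through.** **Inputs from the plan.** 240/2 = 120 per arm; 16 segments; at least two abnormal; level 0.05; WMSI at 3, 6 and 12 months. The plan gives no power, effect size, SD, correlation or recovery rate, so there is no figure of its own to reproduce. Everything below that needs such a figure is an assumption, and tests are taken as two-sided.

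**1. Largest possible decrease.** Assume scores of 1 normal, 2 hypokinetic, 3 akinetic. With k abnormal segments each scored s, WMSI = [(16 − k) + k·s]/16, and the largest decrease is WMSI − 1.

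| Abnormal segments | WMSI | Largest decrease |
|---|---|---|
| 2 hypokinetic | 18/16 = 1.125 | 0.125 |
| 2 akinetic | 20/16 = 1.25 | 0.25 |
| 4 akinetic | 24/16 = 1.50 | 0.50 |
| 6 akinetic | 28/16 = 1.75 | 0.75 |
| 8 akinetic | 32/16 = 2.00 | 1.00 |

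Six akinetic segments allow six times the decrease of two hypokinetic ones; eight allow eight times.

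**2. Independent recovery.** Assume 2 to 10 abnormal segments with equal probability (mean 6), half akinetic, each segment recovering independently, no reading error. Mean excess is 6 × 1.5 = 9 points, or 9/16 = 0.5625. Ten points more recovery gives an arm difference of 0.10 × 0.5625 = 0.056. Simulated standard errors, with power ≈ Φ(0.056/SE − 1.96):

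- 50% v 60%, unadjusted: SE 0.0238; 0.056/0.0238 − 1.96 = 0.39; power about 65%.
- 50% v 60%, adjusted: SE 0.0156; 0.056/0.0156 − 1.96 = 1.63; power about 95%.
- 40% v 50%: SE 0.0214 unadjusted and 0.0156 adjusted; power about 74% and 95%.

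**3. Segments that recover together.** Let the recovery probability vary between patients and add reading error of SD 0.05 to each echo.

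| Recovery | Within-patient correlation | Unadjusted | Adjusted |
|---|---|---|---|
| 50% v 60% | 0.1 | 50% | 77% |
| 50% v 60% | 0.2 | 45% | 65% |
| 50% v 60% | 0.33 | 39% | 53–55% |
| 50% v 60% | 0.4 | 37% | 49% |
| 40% v 50% | 0.2 | 51% | 66% |
| 40% v 50% | 0.4 | 41% | 51% |

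A separate model had 2 to 8 abnormal segments, recovery by score point rather than by segment, and the same reading error. At 40% v 50% it gave 42–62% unadjusted and 53–84% adjusted. Over all settings with these recovery rates the gain ran from about 6 to about 30 points.

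**4. Bias and type I error.** In that separate model the mean arm difference was the same with and without adjustment (about 0.046 to 0.048). With no true effect, the unadjusted test rejected in 4.4% to 5.7% of runs.

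**5. Chance imbalance.** In the model of step 2, excess = k + Binomial(k, ½). Its variance is 1.5² × 6.67 + 6 × 0.25 = 16.5, so baseline WMSI has SD √16.5/16 = 0.254. The difference in arm means then has SD 0.254 × √(2/120) = 0.033. With about half the excess recovering, a one-SD imbalance moves the unadjusted difference by 0.5 × 0.033 ≈ 0.017, about 30% of 0.056.

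**6. Check without a recovery model.** With equal variances at baseline and follow-up and correlation ρ, the variance of change relative to ANCOVA is 2(1 − ρ)/(1 − ρ²) = 2/(1 + ρ): 1.54, 1.33 and 1.18 at ρ = 0.3, 0.5 and 0.7. For a true difference of 0.362 SD of WMSI and 120 per arm, power is 66% v 84%, 80% v 90% and 95% v 98%. The last gain is small because power is already near its ceiling.

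**The case against.** The strongest reply is that randomisation already protects this comparison. A reader might infer from the ceiling arithmetic that baseline extent hides or distorts the treatment effect. The documents do not support that. Allocation between FCM and oral iron is random, so baseline WMSI is balanced in expectation, the unadjusted contrast is unbiased, and ordinary chance imbalance is already reflected in its standard error. Step 4 agrees. This stands, and it limits the point to precision. It does not extend to the normal-iron group, which is not randomised.

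A reader might also infer that most of the spread in the decrease comes from baseline extent. That is model-dependent: baseline explains about 56% of the variance with independent recovery at 50% v 60%, 46% at 40% v 50%, and only about 18% to 39% once segments within a patient recover together, which is plausible within one infarct territory. The 30-point gain is therefore the favourable end.

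Third, the plan does not say that the decrease will be analysed unadjusted. That is inferred from silence, and a decrease can be analysed with baseline as a covariate. This also stands, but it favours writing the analysis down.

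Finally, two hypokinetic segments is the minimum for entry, not the typical patient, and Table 1 with the eligibility criteria is not in the text available, so a further wall-motion limit cannot be excluded. A narrower range would reduce the gain.

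**Conclusion.** The point holds as one of efficiency and incomplete specification. The plan names a decrease in WMSI as primary but states no adjusted comparison and no visit. Read naturally, it would discard baseline information that every patient already provides. The result would be a valid but less precise comparison, more exposed to chance imbalance in screening WMSI.

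The direction is firm: adjustment gained power in every setting with a true effect, and 2/(1 + ρ) exceeds 1 for any ρ below 1 when variances are equal. The size is not firm, since it rests on assumed scoring, segment distribution, recovery rates, within-patient correlation and reading error. A conclusion that the randomised comparison is invalid, or that the sponsor deliberately chose an unadjusted analysis, would go beyond the documents. This should be changed, but it does not threaten the validity of the trial.

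**What to change.** Name one of the existing 3-, 6- or 12-month visits as primary. State that FCM and oral iron are compared on WMSI at that visit by ANCOVA, with treatment arm and screening WMSI in the model, reporting the adjusted mean difference with its confidence interval.

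The word decrease can stay if preferred. With D = B − F (B screening, F follow-up), regressing D on arm and B gives the same arm effect as regressing F on arm and B, with the sign reversed. Visit and model should be fixed before WMSI is looked at by arm.

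Stratifying the blocks by screening WMSI is optional, and only if randomisation has not started; the covariate delivers most of the gain, and the documents support no particular cut-point. The entry criterion need not change.

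The cost is a sentence or two in the Study outcomes and Statistical analysis paragraphs, plus separate randomisation lists if stratification is adopted. No additional visits, readings or patients are required.

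### Are the HF component, the follow-up clock and the treatment comparison for the secondary composite too loosely defined to analyse?

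*Combined protocol and SAP*

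**What the plan says.** All the relevant text is in the Methods section of the combined protocol and SAP.

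- **Endpoint** (Study outcomes): "The secondary outcome the composite of cardio-vascular (CV) mortality, non-fatal stroke, non-fatal MI, recurrent HF hospitalizations". No component is defined further and no counting rule is given.
- **Population** (opening paragraph): "360 patients, with or without ID, hospitalized with MI are recruited". The qualifying admission is therefore for MI.
- **Randomised comparison**: "Patients with ID (n=240) are randomised (1:1) to either intravenous (i.v.) FCM or oral ferrous sulphate", which gives 120 per arm. A further 120 patients with normal iron status form a non-randomised control group.
- **Follow-up** (Patient Assessments): "All participants are observed for 12 months from the first visit after the admission to the study". The visits are set out as "Participants are evaluated in-person at 3-, 6-, and 12-month intervals", with monthly telephone contact, and "Primary and secondary outcomes are established during follow up period".
- **Earlier time points**: screening takes place within 24 hours after MI. For FCM, "Patients receives all doses during hospitalization".
- **Analysis** (Statistical analysis): counts and percentages of subjects, Kaplan-Meier curves by unspecified subgroup for associations with outcomes, and a 0.05 level for tests that are not named.

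**The concern.** Three gaps meet in one endpoint.

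1. **Event.** With an index stay for MI, *recurrent* has no stated reference. It could mean (a) any HF admission after the index stay, (b) only a second or later HF admission, or (c) every admission, totalled. Under (b), a patient's first-ever HF admission would not count.
2. **Window.** Follow-up is not tied to randomisation. If the clock opened at some visit after the hospital stay, in-hospital events would be missed, and a randomised patient who died before that visit would contribute nothing. That would damage the randomised comparison as well as its precision.
3. **Comparison.** There are three groups, one of them not randomised, and the plan does not say which are compared on this endpoint or by what measure.

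The first two decide who has an event, so a later choice of test cannot repair them. In an open-label trial, leaving them open could allow a choice made with sight of the results by arm.

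**Working it through.** The plan gives no event rate, effect size or power, so it has no figure of its own to reproduce. The counts agree: 240 + 120 = 360, and 240 / 2 = 120 per arm.

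**Which readings fit the text**

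- *Event.* Counts of subjects and Kaplan-Meier curves are per-patient tools, which argues against (c). They do not separate (a) from (b), but the composite itself does. Reading (b) would count a first stroke and a first new MI while ignoring a first HF admission. In patients admitted with MI, (a), HF admission after the index stay, is the natural meaning.
- *Window.* The only visit described before month 3 is screening. A clock starting there ends at month 12, the last listed visit. A clock starting at the month-3 visit would end at 3 + 12 = month 15, when no visit is planned. A start one or two weeks after MI matches no visit in the plan. Timing from screening rather than randomisation causes no bias between arms, because nothing that happens before allocation can depend on the arm.
- *Comparison.* Only one randomised contrast exists, FCM versus oral iron. With Kaplan-Meier curves and a 0.05 level, the log-rank test is the default.

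**Size under reading (b)** (all rates are assumptions)

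HF admissions per patient-year are negative binomial with mean m and dispersion k (Poisson if k = 0). The share with an earlier HF admission is h, and the independent 12-month risk of another component is q.

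- P0 = (1 + km)^(−1/k); P1 = P0 × m / (1 + km)
- Reading (a): A = 1 − P0
- Reading (b): B = hA + (1 − h)(1 − P0 − P1)
- Patients with a composite event: d = 240 × [1 − (1 − q)(1 − A)], or with B in place of A

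Mid case, m = 0.1, k = 1, q = 0.10: P0 = 0.9091, P1 = 0.0826.

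| | HF patients | Composite d | 95% CI around HR 0.80 |
|---|---|---|---|
| (a) | 240 × 0.0909 = 21.8 | 240 × (1 − 0.9 × 0.9091) = 43.6 | 0.44–1.45 |
| (b), h = 0 | 240 × 0.0083 = 2.0 | 240 × (1 − 0.9 × 0.9917) = 25.8 | 0.37–1.73 |
| (b), h = 0.3 | 240 × 0.0331 = 7.9 | 240 × (1 − 0.9 × 0.9669) = 31.1 | 0.40–1.61 |

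The interval is 0.80 divided and multiplied by exp(1.96 × 2/√d), a factor of 1.81, 2.16 and 2.02 in turn.

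Over m = 0.05–0.4, k = 0–3, h = 0–0.3 and q = 0.05–0.15, the ratio of (b) to (a) runs from 19.9/69.4 = 0.29 (m = 0.29, k = 0, h = 0, q = 0.05) to 39.4/45.3 = 0.87 (m = 0.05, k = 3, h = 0.3, q = 0.15).

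**Information under the favourable reading**

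Assume a 20% 12-month risk on oral iron and a hazard ratio of 0.7. The FCM risk is 1 − 0.8^0.7 = 0.145, giving 120 × (0.20 + 0.145) ≈ 41 events. Schoenfeld power is Φ(√41.4/2 × |ln 0.7| − 1.96) = Φ(−0.81) ≈ 21%. About 247 events would be needed for 80% power.

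**The case for a change.** The strongest case for action is that the favourable readings are inferred and nowhere written down, and that an open-label trial should not leave them to inference. Asking for the wording costs almost nothing. The factual part of this stands: *recurrent* has no stated reference, the start of follow-up is clumsily expressed, and no contrast or effect measure is named.

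A late clock could also do real harm if it were used. Take a 12-month risk of 25% (60 of 240) and a start at day 14, with a full 12 months counted from there. Under a constant hazard, 2.6 events fall before the start, but later events nearly replace them, leaving 59.3 counted. Under a strongly front-loaded hazard (Weibull shape 0.5), 13.1 fall before the start and 47.8 are counted. Losing early deaths would be a fault whatever the total.

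This does not carry the point, because no visit in the plan supports such a start. The front-loaded shape is also an assumption that the documents do not inform. The missing comparison is not particular to this endpoint either: the Statistical analysis paragraph names none for the primary WMSI outcome. Data capture gives no separate ground for concern, since "The data of each study participant will be entered into individual patient registration cards specially designed for each visit" and patients are telephoned monthly. The documents do not show, however, whether those cards record event dates.

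**Conclusion.** No change to the plan follows. The endpoint is described too briefly, but the gaps are ones a competent analyst fills in the same way: any HF admission after the index MI stay, time to first event, a clock from the screening visit, and the two randomised arms compared by log-rank test with the normal-iron group shown descriptively. On that reading no event and no randomised patient is lost.

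The loss to 29–87% of patients with a composite event arises only if second or later HF admissions alone count, and every rate behind it is assumed. Even then the inference hardly moves: an interval of 0.44–1.45 and one of 0.37–1.73 are both compatible with substantial benefit and substantial harm.

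The conclusion rests on two things: the visit schedule fixing the start of follow-up at or near screening, and the composite treating its non-fatal components alike. It would change if there were evidence that the sponsor meant to ignore first HF admissions or to start counting after discharge. The documents contain none.

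### The primary WMSI outcome has no planned between-arm analysis; comparing FCM with oral iron at one named visit, adjusted for screening WMSI, would gain precision at almost no cost

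*Combined protocol and SAP*

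**What the plan says.** The Study outcomes paragraph of Methods defines the primary outcome in one sentence: "The primary significant outcome is the decrease in WMSI value". It gives no visit, contrast or effect measure.

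Under Patient Assessments, "Participants are evaluated in-person at 3-, 6-, and 12-month intervals" and "Echocardiography with WMSI evaluation, KCCQ, CBC, serum iron level, TIBC, serum ferritin level, TSAT is performed during every physical evaluation visit", so follow-up WMSI exists at three time points. The only statement on timing of the outcome is "Primary and secondary outcomes are established during follow up period".

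The Statistical analysis paragraph is the whole analysis plan. For continuous data it says "For continuous variables, the mean, median, standard deviation, first and third quartiles, and minimum and maximum values will be presented". It continues "Clinical-laboratory associations will be assessed as well as associations with outcomes (Kaplan-Meier subgroup survival curves" and ends with "The level of significance to be used for tests will be 0.05".

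The opening paragraph of Methods describes an open-label trial in which 240 iron-deficient patients are randomised 1:1 to FCM or oral ferrous sulphate. A further 120 patients with normal iron status, who are not randomised, are called the control group.

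**The concern.** A 0.05 level implies tests, but none is named. Descriptive summaries do not compare arms, and Kaplan-Meier curves do not compare a continuous decrease. So nothing in the plan says how the randomised comparison on the primary outcome will be made.

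Two things are at stake.

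- **Precision.** Subtracting the screening value fixes its coefficient at 1, whatever the data show. Estimating that coefficient by ANCOVA uses the same measurements at least as efficiently in large samples. Both approaches target the same treatment difference under randomisation, so bias is not the issue.
- **Freedom of choice.** With three visits and no stated method, the visit and the choice between adjusted and unadjusted results could be settled after unblinded data are seen. If three visits were each tested at 0.05 and were independent, the chance of at least one false positive would be 1 − 0.95³ = 14.3%. Correlated visits would give less.

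**Working it through.** **Inputs from the documents.** 240 patients randomised 1:1, so n = 240/2 = 120 per arm; 240 + 120 = 360 agrees with the stated total. Level 0.05, taken as two-sided because the plan does not say. There is no power statement, target difference or SD to reproduce.

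**Assumed inputs.** Screening SD = 1 (the unit); follow-up SD = k; correlation between screening and follow-up WMSI = r; complete data.

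**Is a screening WMSI available?** Screening lists echocardiography within 24 hours of the MI but does not name WMSI. Eligibility depends on segmental wall motion on an echo in the same window, and Methods makes WMSI the measure of LV systolic function. A decrease also needs a starting value. Availability is therefore a well-supported inference, not a stated fact.

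**Formulas (per-patient variance).**

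- Raw decrease: Vc = 1 + k² − 2rk
- Adjusted for screening value: Va = k²(1 − r²)
- Difference: Vc − Va = (1 − rk)², never negative, and zero only when rk = 1
- With k = 1: Va/Vc = (1 + r)/2
- 95% CI half-width for the arm difference: 1.96 × √(2V/120)
- Raw-decrease sample size giving the same precision: 120 ÷ (Va/Vc)

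**Equal SDs (k = 1).** Half-widths are in screening-SD units.

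| r | Vc | Va | Va/Vc | Half-width, raw | Half-width, adjusted | 120 per arm is worth |
|---|---|---|---|---|---|---|
| 0.3 | 1.40 | 0.91 | 0.65 | 0.299 | 0.241 | 185 |
| 0.5 | 1.00 | 0.75 | 0.75 | 0.253 | 0.219 | 160 |
| 0.7 | 0.60 | 0.51 | 0.85 | 0.196 | 0.181 | 141 |
| 0.9 | 0.20 | 0.19 | 0.95 | 0.113 | 0.110 | 126 |

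If the raw comparison had 80% power, the adjusted one would have 93.5%, 89.9%, 86.0% and 82.0% in these four rows.

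**Unequal SDs, Va/Vc.**

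| k | r = 0.3 | 0.5 | 0.7 | 0.8 | 0.9 |
|---|---|---|---|---|---|
| 0.75 | 0.460 | 0.519 | 0.560 | 0.559 | 0.503 |
| 1.25 | 0.784 | 0.893 | 0.981 | 1.000 | 0.950 |

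The extremes: at k = 0.75, r = 0.3, 0.5119/1.1125 = 0.460; at k = 1.25, r = 0.8, 0.5625/0.5625 = 1.000.

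**Price of estimating the slope.** With 240 patients and a normal baseline, the variance factor is 1 + 1/(240 − 4) = 1.0042. The worst case, at rk = 1, is thus a loss of about 0.4%.

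**Simulation.** With 20,000 trials of 120 per arm, the ratios at k = 1 were 0.655, 0.765, 0.851 and 0.954 for r = 0.3, 0.5, 0.7 and 0.9. They were 1.005 at k = 1.25, r = 0.8 and 0.453 at k = 0.75, r = 0.3. A separate run of 5,000 trials per scenario gave ANCOVA type I error rates of 0.048 to 0.054.

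**The outcome can remain a decrease.** If follow-up = a + b·arm + c·screening, then screening − follow-up = −a − b·arm + (1 − c)·screening. The treatment effect is the same apart from its sign.

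**The case against.** The strongest reply is that the comparator is supplied by the reviewer. The plan never says raw decreases will be compared; within-arm change, a responder count or a three-group test would be equally consistent with it. On that view the documented defect is the missing analysis, and the ANCOVA gain is measured against something nobody planned. The first part stands: the plan does not commit to a raw comparison, and the omission needs no arithmetic to establish. But the decrease is the outcome as worded, and the sponsor must write some comparison, so it matters which one is better.

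The size is also open to challenge. The 35% to 5% range depends on equal SDs; at k = 1.25 the reductions are about 11%, 2%, 0% and 5% for r = 0.5, 0.7, 0.8 and 0.9. Variance also looks more impressive than interval width: at k = 1 the half-width shrinks by about 19%, 13%, 8% and 2.5%. This stands as a limit on what can be claimed, not on the direction of the gain.

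The 0.4% figure assumes a normal baseline, whereas eligibility restricts screening WMSI from below. A simulation with a skewed, bounded baseline gave a worst-case cost of about 0.2%, so this does not change the picture.

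Finally, the figures assume all 240 patients have a follow-up echo, and deaths will leave some without one. That gap is real, but it affects any WMSI analysis and adjustment does not resolve it.

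**Conclusion.** The point holds. No between-arm model, visit or covariate is tied to the primary outcome, and that follows from the text alone. In large samples under 1:1 randomisation, adjusting for screening WMSI cannot be less precise than comparing raw decreases.

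The size in this trial cannot be known from the documents. For k from 0.75 to 1.25 and r from 0.3 to 0.9, the variance ratio runs from 0.46 to 1.00. The gain is nil where the slope of follow-up on screening WMSI is 1. These figures rest on assumed SDs and correlations, complete data and a WMSI recorded at screening. They apply only to the 240 randomised patients. Naming one visit adds no precision; its value is in closing off a choice. The change is worth making, but the lack of adjustment does not in itself threaten validity.

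**What to change.** Add one primary analysis to the Statistical analysis paragraph:

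- **Population and contrast:** FCM versus oral ferrous sulphate in the 240 randomised iron-deficient patients, analysed as randomised. State that the normal-iron group is not part of this contrast; its label as control group makes this necessary.
- **Model:** ANCOVA of WMSI (or of its decrease) at one named visit, with screening WMSI as covariate. Report the adjusted difference with a 95% CI and state that the 0.05 level is two-sided, if that is intended.
- **Visit:** the sponsor's choice, fixed in advance. Month 12 is a natural candidate, since "All participants are observed for 12 months from the first visit after the admission to the study".
- **Baseline:** state in the Screening paragraph that WMSI is recorded from the screening echo.
- **Supportive analysis, optional:** a repeated-measures model over months 3, 6 and 12 with the same named-visit contrast.

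A rule for deaths and missing echoes is needed as well, as a separate item.

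The cost is SAP wording, with no new patients or visits. If full segment scoring was not already intended at screening, it would have to be recorded from an echo that is done anyway.
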